A recent meta-analysis of RCTs in the ED found evidence that one-session alcohol BIs reduce alcohol use among hazardous drinkers,⁶ but the effects were smaller than those in primary care.⁴ One-session BIs have not had a large effect on individuals with more serious alcohol problems. Further, following an alcohol BI in the ED, few patients who needed more intensive specialty alcohol treatment services received it.⁷ Recent data indicates that telephone monitoring and brief care management are potentially effective higher intensity options to overcome barriers to substance use treatment, demonstrating the promise of these approaches.²⁹ Given the constraints of existing ED provider resources, peer support specialists could serve a vital role in delivering BIs plus additional supportive contacts for Veterans with hazardous or harmful alcohol use detected in the ED. *This study will use structured 6-session post-ED visit peer mentoring compared to a 1-session ED-based clinician brief advice intervention. If the peer mentoring SBIRT (including additional post-ED contacts and support) is found to be more efficacious compared to clinician brief advice conducted in the ED, it will answer the pressing question regarding whether peers should be allocated to provide SBIRT assistance in the VA ED setting, with the benefit of ongoing structured contact that a caring, engaged peer can provide to extend the potential impact of brief interventions and increase motivation to change. If successful, this can both expand the use of peers who have lived experience that is directly related to the issues facing many Veterans seeking ED care, and will free up clinicians to address other critical emergent clinical Veteran concerns.*

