Description of Study Site. The proposed study will recruit from the ED in the VA Ann Arbor Healthcare System (VAAAHS). The following numbers are based on data from 2015. This ED treated a total of 10,653 patients drawn from a relatively wide geographic area that included western Wayne County (Detroit area), as well as several mid-sized cities and rural communities. Patients seen had the following characteristics: 9% female; 75% White, 10% African American, and 3% of another race (mainly multiple races); about 2% Hispanic. The VAAAHS ED is very supportive of this research project. Only one site will be included in this study to enhance our ability to ensure fidelity of peer-delivered intervention content through closer supervision and monitoring. If shown to be efficacious, we will scale up in order to add many sites later through an implementation study.

Inclusion Criteria for Screening. (1) adults age 18 years of age or older presenting for care in the Ann Arbor VHA ED; and (2) medically stable and able to provide informed consent per Mini-Cog assessment score of 3 or more.

Inclusion Criteria for the RCT. *Individuals will be eligible to participate in the RCT if they: (1) have an AUDIT-C score of 4 or more for men and 3 or more for women in the prior 3 months, indicating that they meet criteria for hazardous use⁵⁵; and 2) have a telephone and/or the ability to provide information about individuals who can help contact the participant. Homeless Veterans may not have a telephone but will be asked for individuals who can help to contact them (e.g. shelter, family, friends, etc.). Importantly, the study will include not only those with less severe hazardous drinking but also those with more harmful use and severe problems to address the problems and needs of Veterans who can most benefit from linkage to primary and secondary care. Furthermore, a recent study validates the full AUDIT among Veterans, with scores of 14 and 10 (male, female, respectively) indicating an AUD.⁵⁶ However, to be inclusive and sure that all Veterans who may need specialty care have the information to get to that care, we will set scores for specifically recommending specialty care to the Veteran participant more conservatively at 10 for men and 8 for women.* Both study conditions will receive information on accessing VHA primary/specialty services.

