ED Staffing / Subject Accrual. Because it is not possible to staff the project continuously (168 hours/week), this study will use the following sampling frame that has been used successfully in our previous ED research to ensure obtaining a representative sample of Veterans presenting to the AAVA ED. Project staff in the ED will recruit patients for the study 5 days per week between the hours of 10AM to 6PM. The majority of the recruitment time will be spent in the ED between 10AM and 6PM because 65-70% of patients enter the ED during those hours. In addition, another three days/week will include a weighted sampling of recruiting between either 7AM-3PM or 3PM-11PM time period. Thus, a total of 8 shifts (8 hours each) will be staffed each week to recruit, consent, screen patients, conduct baseline assessments, and deliver brief advice. Based on our previous ED studies where we have used similar staffing schedules we expect to accrue the following numbers: 30 months of screening x ~130 patients/month approached = 3,900; it is expected that 80% (n=3,120) will agree to participate and will be screened. We conservatively expect that 15% of the screened patients will have a positive screen and will be randomized (450 randomized; 225 per group). Randomization Procedures. Stratified random assignment to conditions will be by sex and presence of an AUD (yes/no) defined as a score of 14 for men and 10 for women on the AUDIT. Randomization by sex will be used because men and women generally differ in their rates and nature of alcohol use, problems, and outcomes. Random assignment will also be stratified based on meeting criteria for past year AUD (yes/no) because of potential differences in problem severity and potential intervention response. Randomization will proceed in blocks of 10 within study cells, in order to equalize randomization over time. Follow-up staff will be blind to condition. Participants in both conditions will receive written information regarding alcohol and VHA resources and be re-contacted to complete 3-, 6-, and 12-months follow-ups.

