Data Management. The project's data manager will conduct all data management and analysis activities under the supervision of Drs. [name] and [name]. Research staff will use double entry procedures and reconcile discrepancies. Data cleaning will be conducted throughout data collection to ensure a quality final dataset for analysis. Statistical Analysis System (SAS) will be used to examine and prepare data for the analysis.

General analytic approach. Hypotheses will be planned a priori, and will be limited to the examination of a limited number of outcomes. We will utilize an "intent-to-treat" approach. All analyses will use two-sided tests because it is possible that the APM participants might have worse outcomes compared to CBA participants. Analyses will begin with descriptive data analyses to determine distributions of key variables, to collapse categories, if necessary, and to review data for outliers and clear anomalies. Tests for linearity, independence, missingness, and distributional assumptions will also be performed. Normalizing transformations of the dependent variables will be utilized, if necessary. We will validate the randomization scheme by comparing the initial groups on key variables that could be associated with the outcomes. Where we identify significant differences between groups, we will adjust for these variables, as well as other addictions treatment received if it was not initiated by referral from the APM or CBA clinician (and thus a potential mediator of effect). Prior to fitting any analytic models, a graphical exploration of the outcome variables will be conducted to select the appropriate models based on variable distributions.

Missing data. Every effort will be made to minimize missing data. Where we have missing covariates that are necessary for analysis, we will perform multiple imputation of missing data and combine the results from 5 imputations based on Rubin's method to produce an estimate and the corresponding confidence interval accounting for missing data uncertainty.⁸⁸ For follow-up attrition, the proposed mixed-effects regression model will allow the use of data from all participants (not just those with complete follow-up) and provide unbiased

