parameter estimates that account for missing data under the missing-at-random assumption.⁸⁹ We will look for non-random attrition, and if we find, for example, attrition rates to depend on a baseline covariate, we will include this covariate in the model. If we find attrition to depend on treatment use or ideation at prior assessments, we will utilize an appropriate pattern mixture model or multiply impute data based on an appropriate pattern mixture model assumptions based on the observed missing data pattern.⁸⁸

Aim 1: Determine the efficacy of the ED APM intervention compared to BA on TLFB drinking frequency reports at 3-, 6-, and 12-months post-baseline. **Hypothesis:** Veterans with hazardous drinking who are randomly assigned to APM will have significantly greater reductions in total TLFB drinking frequency reports, compared to those assigned to CBA.

Data Analysis for Aim 1: The primary purpose of Aim 1 is to examine the impact of the intervention on frequency of drinking per TLFB interview. This outcome will likely follow the assumptions required for linear regression model, but we will adjust the model type as needed. Assuming this is the case; we will use a linear mixed-effects model and estimate the treatment effect as the difference in the time-averaged TLFB frequencies over the year of follow-up. Because reduction in problem alcohol use is of primary interest, the analysis will model change-scores from baseline in the response variable as dependent variable, and the independent variables will include the baseline values of the response variable, time in months since randomization, and the treatment group indicator. The parameter estimate of the treatment group indicator will estimate the time-averaged treatment effect. *In a second model, we will include an interaction of time by treatment group indicator to formally test the possibility that the effect varies over time. Models will include a random effect for which specific peer/clinician a participant was assigned.*

Aim 2: Determine the impact of the APM intervention on linkage to primary and specialty alcohol treatment services care, mental health symptoms and functioning at 3-, 6-, and 12-months post-baseline, compared to BA. **Hypothesis:** Veterans with hazardous drinking who are randomly assigned to APM will be significantly more likely to engage in primary, specialty care, and other VHA supportive services and to have improvements in mental health symptoms and functioning.

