Data Analysis for Aim 2: The focus of Aim 2 is to study intervention effects on secondary outcome of frequency of primary care and mental health specialty care visits (as two separate outcomes) from the TSR, calculated as an average number of visits per month during each follow-up period. Similar to Aim 1, analyses will generally use a mixed effect model framework. As described above, initial analyses will examine the distribution of outcome measures over follow-up in order to select an appropriate model (e.g. Poisson regression or a related method for counts of visits). Our analysis strategy will parallel Aim 1 in terms of the independent variables, *random effect for peer/brief advice, focus on time-average treatment effects, and additional modeling of interactions of group and time.*

Secondary Aim will determine the mediators (e.g., motivation to change, self-efficacy, coping, social support) of the effect of the intervention and linkage on subsequent alcohol use and alcohol-related consequences. **Hypothesis:** The effect of randomization to APM compared to BA on the primary outcomes (i.e., alcohol consumption and consequences) will be mediated by differences between groups in motivation to change, self-efficacy, and perceived helpfulness of peer support.

Data Analysis for Secondary Aim: *In order to establish temporal ordering, we will examine whether level of the hypothesized mediators at 3 and 6 months post-baseline mediates the effect of random assignment on 6- and 12-month measures of the three primary outcomes of alcohol use behaviors.^{90,91} We will first determine the whether study condition is associated with the hypothesized mediators over the first six months of follow-up and check for a direct effect of the mediators at 3 and 6 months on alcohol use as measured at 6- and 12-months follow-up. We will estimate the indirect effect of the intervention on alcohol use through the mediators and conduct significance testing of this effect using macros created by Preacher and Hayes.⁹²*

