Data Analysis for Exploratory Aim: Interviews will be audiotaped and transcribed verbatim for content. We will conduct analyses. We will use a rapid data analysis process, a technique used when there is a need for targeted, actionable information.⁹³ The research team will read early transcripts independently, and, in an iterative process, meet to develop and refine the coding scheme and code definitions, including developing new codes from the data based on ongoing data analysis. We will document code definitions, data interpretation, and analytic decisions in memos. Once the research team has agreed on codes and code definitions, Drs. [name] and [name], and the research supervisor, will independently review and code transcripts, meeting regularly to compare coding results, and resolving discrepancies through a consensus process. If coding definitions are refined during this process, the coders will recode transcripts already coded. Once data are coded, we will use QSR NVivo 10 software to organize the data. The study team will meet regularly to discuss code summaries and memos, developing findings with a focus on barriers and facilitators to implementation and potential testable implementation strategies. Members of the study team have used similar methods in a study of the acceptability of peer support interventions in Michigan NG soldiers.^{94,95}

Power and Sample Size Calculations

Of 450 participants randomized, we expect that at least 80% of participants will be retained (n=360). We conservatively have estimated power without accounting for methods that will allow inclusion of participants with partial follow-up data because this benefit will be off-set to an unknown degree by the additional parameters estimated in a mixed effects model. All power analyses used G*Power 3.1.9 software and a two-sided $\alpha = .05$. We calculated power based on several potential outcome measure distributions. If a linear model is appropriate, which we expect to be the case for the primary outcome of total AUDIT scores, we achieve 80% power to detect an effect size (Cohen's d) of 0.30. This is a relatively modest and reasonable effect size for studies of SBIRT models of alcohol brief interventions. For an outcome with a count distribution and assuming a mean level in controls of 1 (e.g., an average of 1 alcohol-related treatment visit in a follow-up period), we achieve 80% power to detect an incidence rate ratio of 0.75 or 1.34 under a Poisson framework.

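### The 80% power figure treats 360 participants as independent, but the primary model has a provider random effect whose number of levels, intraclass correlation and degrees-of-freedom method are not stated

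*Combined protocol and SAP*

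**What the plan says.** **Model.** Data Analysis for Aim 1 uses a linear mixed model for change from baseline, with baseline value, time and treatment group as predictors. It adds: "Models will include a random effect for which specific peer/clinician a participant was assigned". Data Analysis for Aim 2 carries this over ("random effect for peer/brief advice, focus on time-average treatment effects"). This is the only random effect named. The Missing data paragraph says that "the proposed mixed-effects regression model will allow the use of data from all participants", which probably implies a participant-level term, but none is specified.

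**Power.** Power and Sample Size Calculations takes 450 randomised and 80% retained (360), with two-sided alpha 0.05, and states 80% power at Cohen's d = 0.30. It takes no credit for partial follow-up data, on the ground that "this benefit will be off-set to an unknown degree by the additional parameters estimated in a mixed effects model". Providers, clustering, ICC and design effect are not mentioned. The outcome it names is total AUDIT score, whereas Aim 1 and the Measures section make TLFB drinking the primary outcome.

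**Who delivers the advice.** The accounts differ:
- Peer Mentor Content: peers deliver the brief advice in the ED.
- Brief Advice Condition: a research assistant delivers it to the BA arm.
- Background (Alcohol BIs): the comparison is "peer mentoring compared to a 1-session ED-based clinician brief advice intervention".
- Recruitment / Informed Consent: peers staff the ED to give the advice, with no arm named.
- Alcohol Brief Advice Content: the pamphlet, which both arms receive, has space for a peer to tailor it.
- Human Subjects: an ED clinician or the peer mentor, for both conditions.
- Potential Risks: a research assistant or a peer.

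**Numbers of staff.** None is given. The Resources paragraph refers key roles to a budget justification that is not in the file.

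**The concern.** Once the analysis includes a provider effect, the precision of the treatment contrast depends on how providers relate to arms. If each provider serves one arm, the difference between arm means contains the difference between two small averages of provider effects. Further visits or participants do not remove that component; only more providers do. The power figure has no term for it.

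Two things are at stake. The first is whether 80% describes the test that will be run. The second is the validity of that test. With a handful of nested providers the reference distribution matters a good deal, and the plan leaves it open for the primary analysis.

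**Working it through.** **1. The plan's own figure.** Inputs from the power section: 180 per arm, d = 0.30, two-sided 0.05. SE = √(2/180) = 0.1054 and noncentrality = 0.30/0.1054 = 2.85. With 358 df, power is 81.0%, so the figure reproduces for independent participants. The sample size for 80% is 175 per arm (350 in total), so the spare design effect is only 360/350 = 1.03.

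**2. Assumptions for the planned model.** None of these is in the documents:
- three follow-up visits, adjusted for baseline, with every pair of measurements correlated r = 0.6;
- k equal caseloads per arm, nested in arm;
- ICC from 0 to 0.05, as a share of single-visit variance.

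A small k is suggested by one site ("Only one site will be included in this study to enhance our ability to ensure fidelity of peer-delivered intervention content") and by staffing: "a total of 8 shifts (8 hours each) will be staffed each week", which is 64 hours. Turnover over 30 months of recruitment would raise it.

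**3. Nested power, equal ICC in both arms.**
- v = (1 + 2r)/3 − r² = 0.733 − 0.360 = 0.373
- SE² = 2 × [ICC/k + (1 − ICC) × v/180]
- Power from a noncentral t on 2(k − 1) df

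Example with k = 3 and ICC 0.01: SE² = 2 × (0.00333 + 0.00205) = 0.01077, SE = 0.104, noncentrality 2.89. On 4 df the critical value is 2.776 and power is 59%.

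| Providers per arm | ICC 0 | 0.01 | 0.02 | 0.05 |
|---|---|---|---|---|
| 2 | 67% | 30% | 21% | 12% |
| 3 | 93% | 59% | 41% | 23% |
| 6 | 99% | 88% | 74% | 47% |

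For r from 0.4 to 0.7, the ICC 0.01 entries run from 56% to 62% (3 per arm) and 85% to 91% (6 per arm). Detectable d at 80% power for ICC 0, 0.01, 0.02 and 0.05 is 0.24, 0.39, 0.50 and 0.73 with 3 per arm, and 0.20, 0.27, 0.32 and 0.45 with 6.

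Much of the loss with few providers comes from the df. With a normal reference, power at ICC 0.01 would be 82% (3 per arm) and 94% (6 per arm), but step 6 shows what that reference costs.

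**4. Clustering in APM only.** Let a = ICC/k + (1 − ICC) × v/180 and b = v/180. Then SE² = a + b and Satterthwaite df = (a + b)²/[a²/(k − 1) + b²/179]. At ICC 0.01, power is 73% with 3 peers (df 3.8) and 95% with 6. At ICC 0.05 it is 27% and 64%.

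**5. Providers crossed with arm and balanced.** With a common provider intercept, the provider term cancels from the contrast and SE² = 2 × (1 − ICC) × v/180. Power is 99.6% to 99.8% over the ICC range. For a single unadjusted endpoint, as in the plan's own figure, it is 81% to 83%.

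**6. Type I error, nested, with a participant term.** Simulation under no effect used 40,000 runs per cell and REML with provider variance truncated at zero. The Satterthwaite rule uses 2(k − 1) df when the provider variance estimate is positive and participant-level df otherwise.

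| Providers per arm | Reference | ICC 0 | 0.01 | 0.02 | 0.05 |
|---|---|---|---|---|---|
| 2 | Normal | 3.8% | 13.1% | 16.0% | 18.2% |
| 2 | Satterthwaite | 3.1% | 7.2% | 6.9% | 6.0% |
| 3 | Normal | 3.8% | 9.8% | 10.9% | 11.8% |
| 3 | Satterthwaite | 3.0% | 5.4% | 5.3% | 5.0% |
| 6 | Normal | 4.0% | 6.9% | 7.4% | 7.8% |
| 6 | Satterthwaite | 3.3% | 4.8% | 4.9% | 5.1% |

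If the provider intercept is the only random effect and the reference is normal, the error is already 7.4% (3 per arm) and 6.7% (6 per arm) at ICC 0, because repeated visits are treated as independent.

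**The case against.** The strongest reply is that every driver of these figures is assumed, and that the range runs from 12% to above 99%. The plan already handles clustering in the analysis, and its power section is openly approximate. Scripted, computer-guided advice under close supervision makes an ICC near zero plausible, and at ICC 0 with 3 or more providers per arm the assumed model gives 93% or more. BA is a single short session while APM adds up to six, so provider variance may lie mostly in APM, where the loss is smaller. Staff numbers may be in the budget justification.

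Most of this stands, and it rules out two stronger readings. A reader might infer that the trial is underpowered; the documents do not support that, because they fix neither k nor the ICC, and some plausible settings exceed 80%. A reader might also infer that the plan uses an anti-conservative test; it proposes no normal reference and is simply silent.

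The reply does not remove the omission. The caveat in the power section sets one unquantified item against another and does not mention providers. Additional follow-up data reduce participant-level variance but add no providers. A headcount held elsewhere would still be absent from the power calculation and the model.

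**Conclusion.** The point holds as a mismatch between the power calculation and the planned analysis, together with an under-specified primary model. The stated 80% is for independent participants, and for a different outcome (AUDIT, not TLFB), so it is not the power of the planned test. The documents do not show whether the true figure is higher or lower.

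Under the stated assumptions, with 3 to 6 providers per arm, power falls from 93% to 99% at ICC 0 to 23% to 47% at ICC 0.05. The loss is smaller if clustering is mainly in APM, and there is essentially none if providers are crossed and balanced. The choice of reference separates a type I error of about 5% from about 7% to 12% at ICC 0.01 to 0.05. Nesting is the most direct reading of the delivery sections, but not the only one. The change should be made; confidence is medium because k, ICC and r are all assumed.

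**What to change.** **Data Analysis for Aims 1 and 2.**
- Specify a participant random intercept (or a within-person covariance) plus a provider random effect, nested in arm if each provider serves one arm, with Kenward-Roger or Satterthwaite df.
- Say how a participant moved to another peer is coded; the peer hiring and supervision section allows such reassignment.
- Offer arm-specific provider variance as a sensitivity analysis.

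**Power and Sample Size Calculations.**
- State the planned number of providers per arm.
- Restate power or the detectable effect for that model over ICC 0 to 0.05, including APM-only clustering, and the crossed case if it applies.
- State it for the TLFB primary outcome.

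**Delivery of BA advice.** Reconcile the sections listed above, since they define the levels of the random effect and whether they are nested.

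**Cost.** SAP wording and a new power statement; no extra participants. Intervals may widen and the stated power may be less favourable. The small-sample df make the test conservative when provider variance is near zero (about 3% in the simulation). With 2 providers per arm and positive provider variance they still leave about 6% to 7%. The change is therefore an improvement rather than a guarantee, and the plan should say so.
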